Another approach would be to use a reduced intensity or a nonmyeloablative conditioning regimen, which have been reported to extend allogeneic transplant to older patients and patients with other co-morbid medical conditions. We, and others, have shown that reduced intensity stem cell transplantation can be safely utilized in older patients and those with comorbidities in other hematological malignancies. 32-37 Rondelli et al and Kroger et al have reported encouraging data in multi-institutional small studies of reduced intensity transplantation in older patients with myelofibrosis. 30,31 In these retrospective studies with a median age of 54 years, a non-relapse mortality of 10% - 16% and 3 year overall survival of 84% - 85% was reported. Based on these data multiple centers studied reduced intensity allogeneic transplantation in myelofibrosis. Recent analysis of worldwide experience reported to CIBMTR registry showed NRM of 24% and OS of 47% ²⁵. Outcome was significantly inferior with unrelated donor. Similarly high NRM of 53% was reported with unrelated donors in a prospective study done by MPD research consortium. Best results to date with reduced intensity regimen were reported by Kroger et al. NRM was 16% and OS 67% with Busulfan and Fludarabine regimen: however 17% of patients had low risk disease and hence expected to have better outcome. Moreover, 13% of patients needed stem cell boost for graft failure or weak graft or declining chimerism. 31

2.4 Allogeneic transplantation for Myelofibrosis: M D Anderson data:

At MDACC based on encouraging early data, 30,31 we did a prospective study to evaluate the role of allogeneic stem cell transplantation using reduced intensity conditioning regimen of

[figure not shown]

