Myelofibrosis results in extramedullary hematopoiesis, massive hepatosplenomegaly and fibrosis in the marrow and there are several major issues unique to it from transplant perspective. These include high incidence of graft failure and weak graft after transplant necessitating use of stem cell boost²² and organ dysfunction - particularly involving liver - leading to a high incidence of veno-occlusive disease and non-relapse mortality.⁴⁰ A safe agent that can reduce organomegaly and disease burden pretransplant may improve transplant outcome by improving engraftment, reducing organ toxicity and lowering relapse risk. Furthermore, it may allow more patients to become eligible for transplant by improving their performance status. A Jak 2 inhibitor might be the answer.

Jak 2 inhibitors and stem cell transplantation:

Discovery of Jak2 V617F mutation, which makes kinase constitutionally active in patients with myeloproliferative disorders led to development several targeted agents including Pacritinib to inhibit this pathway. Jak 2 is mutated in up 60% of patients with ET and MF and 98% of patients with PV. Even in patients without this mutation, this pathway is overactive. Ruxolitinib, a Jak2 inhibitor, is licensed by FDA for MF reduces splenomegaly, improves constitutional symptoms, and improves survival both in patients with and without Jak 2 V617F. Early data on its usage pre-transplant are conflicting with excellent outcome reported in some studies, but a possible higher complication rate reported in other study. This later study presented as an abstract is difficult to interpret, because complications reported are hard to differentiate from usual complications seen post-transplant. Pacritinib causes less myelosuppression than Ruxolitinib and may be superior to ruxolitinib as a pre-transplant agent to reduce organomegaly and to reduce the disease burden.

Pacritinib:

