6.0 Statistical Considerations

General

This will be a single-arm, Phase II study of pacritinib, fludarabine, and busulfan as a preparative

regimen in allogeneic stem cell transplantation in patients with myelofibrosis. The primary endpoint is progression-free survival (PFS) in patients undergoing matched related or at least 7/8 matched unrelated donor transplant. We will enroll at least 21 evaluable patients, defined as patients who undergo transplant with a matched related or at least 7/8 matched unrelated donor. Patients who do not have a suitable related or unrelated donor will come off study and may receive a transplant from a haploidentical donor. For this reason and because some patients may decide not to undergo transplant after starting the drug, we may need to enroll up to 40 patients to ensure that 21 are evaluable for our primary endpoint.

Endpoints

6.1 Primary End Point (Progression-Free Survival):

Progression-free survival is defined as the time of stem-cell transplant to the time of death or disease progression.

6.2 Secondary End Points:

Neutrophil Engraftment is defined as a sustained ANC \geq 0.5 x 10 $^{\circ}$ /L for 3 consecutive days and evidence of donor chimerism by D+28 (the first chimerism study will be done 3-4 weeks post-transplant).

Platelet Engraftment is defined as a sustained first of three consecutive laboratory values of platelet $\geq 20x109/L$ with no platelet transfusions administered for 7 consecutive days.

Non-relapse mortality is defined as death without disease progression.

Liver response will be defined by the change in the size of the liver measured below the coastal margin in the mid-clavicular line by palpitation.

Spleen response will be defined by the change in the size of the spleen measured below the coastal margin in the mid-clavicular line by palpitation.

Quality of life will be measured by the QOL FACT BMT.

Symptom score will be measured by the MPD symptom score.

Immune recovery will be measured by various cell subsets and cytokine levels.

Primary Graft Failure is defined as failure to achieve an ANC \geq 0.5 x 10 $^{\circ}$ /L for 3 consecutive days by day 28, with <10% cellularity on bone marrow biopsy and no evidence of donor chimerism.

Secondary graft failure is defined as a sustained declined of ANC <0.5 x 10°/L for 3 consecutive days after initial documented engraftment with no evidence of disease progression.

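### Section 6.2 leaves some patients with no donor cells counted neither as engrafted nor as primary graft failure, so the graft-failure rate can be too low

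*Combined protocol and SAP*

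**What the plan says.** Objective 1.7 makes primary and secondary graft failure a secondary endpoint, and section 6.2 gives the definitions.

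- **Neutrophil engraftment:** ANC of at least 0.5 x 10^9/L "for 3 consecutive days and evidence of donor chimerism by D+28". The first chimerism study is planned 3-4 weeks after transplant.
- **Primary graft failure:** the definition begins "Primary Graft Failure is defined as failure to achieve an ANC" of that level for 3 days by day 28, and adds "with <10% cellularity on bone marrow biopsy and no evidence of donor chimerism".
- **Secondary graft failure:** a sustained fall of ANC below 0.5 x 10^9/L for 3 "consecutive days after initial documented engraftment with no evidence of disease progression".

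In section 2.4, the part on major impediments to transplant names the risk directly: "These include high incidence of graft failure and weak graft after transplant". Under Secondary Analyses, section 6.0 plans Kaplan-Meier estimates of time to neutrophil and platelet engraftment. It states no separate method for graft failure.

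**The concern.** A reader of objective 1.7 will take the primary graft-failure rate to show how many patients did not end up with a donor graft. The definition does not deliver that. Its three conditions are joined, and the engraftment definition is not its complement. A patient with no donor cells can therefore drop out of both counts.

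The third condition needs particular care in this disease. These patients come to transplant with a diseased marrow, so residual host marrow could keep cellularity at or above 10% in someone with no neutrophil recovery and no donor cells. The other route is recovery of the patient's own haematopoiesis after the graft is lost.

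What is at stake is a secondary safety outcome that the rationale itself puts forward, in a single-arm trial where few events are likely to be counted.

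**Working it through.** No stated figure needs reproducing. The check is of the logic of the definitions, followed by one division.

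**Inputs (section 6.2).** At day 28, let A = ANC recovered, D = donor chimerism present, C = marrow cellularity below 10%.

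- Engrafted: A and D.
- Primary graft failure: not A, and not D, and C.

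**Step 1. Classify every state.**

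| ANC recovered | Donor chimerism | Cellularity | Class under section 6.2 |
|---|---|---|---|
| Yes | Present | Any | Engrafted |
| Yes | Absent | Any | Neither |
| No | Absent | Below 10% | Primary graft failure |
| No | Absent | 10% or more | Neither |
| No | Present | Any | Neither |

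Rows 2 and 4 are the firm gap: no donor cells, yet not a graft failure. Row 5 is a different matter, taken up in the objection. The rows are logical states; they say nothing about how many patients fall in each.

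**Step 2. Can the secondary definition pick up rows 2 and 4?** It applies only "after initial documented engraftment with no evidence of disease progression". Engraftment needs donor chimerism, which these patients lack at day 28. They can become secondary graft failures only if engraftment is first documented.

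**Step 3. Direction.** Everyone meeting the current definition is donor-negative, but not every donor-negative patient meets it. The current count is therefore at most the number of donor-negative patients. Measured against that number it can be too low and cannot be too high.

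**Step 4. Size per patient.** With the planned 21 evaluable patients, one missed case changes the rate by 1/21 = 0.048, or 4.8 percentage points. The documents give no frequency for rows 2 and 4, so the number of missed cases, and hence the total shortfall, cannot be computed.

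**The case against.** The strongest reply is that nobody is lost from the trial's results. Patients in rows 2 and 4 remain non-engrafted in the Kaplan-Meier analysis, and some host recovery may be recorded as relapse or progression. That stands, and it limits the point to the graft-failure rate. It does not remove the point, because the engraftment curve does not show which non-engrafted patients lost the graft.

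A reader might infer several stronger things that the documents do not support:

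- **That everyone not engrafted should count as graft failure.** Section 2.0 names weak graft alongside graft failure as a separate item: "high incidence of graft failure and weak graft after transplant necessitating use of stem cell boost". Keeping donor-positive patients out of graft failure fits that usage. Counting them would also turn a donor-positive patient who recovers on day 29 into a failure.
- **That any short neutropenia counts as secondary graft failure.** The definition asks for a sustained decline and for no disease progression. It has no chimerism criterion, so retained and lost grafts are not separated, but an inflated rate is not shown.
- **That these patients can never become secondary failures.** The secondary definition sets no deadline of its own for documenting engraftment, and the D+28 limit in the engraftment definition can be read as attaching to chimerism only. A donor-positive patient with late neutrophil recovery might then qualify.
- **That the shortfall can be sized from section 2.3.** The figure there, "13% of patients needed stem cell boost for graft failure or weak graft or declining chimerism", is boost use in another study. It is not a graft-failure rate, and no comparison with it is planned.
- **That no marrow is available near day 28.** The marrows at about 3 and 12 months in section 5.4.2 are additional to standard practice, which section 5.4.1 says monitors engraftment. An earlier marrow may well be done.
- **That the safety data cannot show graft failure.** Section 8.0 keeps adverse events known to be related to the transplant out of PDMS, but also says protocol-specific data are entered there. Graft failure is a protocol endpoint, so the text does not settle this.

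**Conclusion.** The concern holds in a limited form. As written, donor-negative patients who recover their own counts, or whose marrow is at least 10% cellular, are neither engrafted nor primary graft failures. The rate for objective 1.7 can be too low by 4.8 points for each such patient at N = 21, with the total unknown.

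This rests on reading the three conditions as jointly required, which is the plain sense of the sentence, and on 21 evaluable patients; with more, each case weighs slightly less. The primary PFS analysis and the sample size are unaffected. It should be corrected before analysis, because a handful of cases could change how the secondary result reads.

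**What to change.** Change the wording in section 6.2, for endpoint classification only:

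1. **Primary graft failure:** patients alive at D+28 with no evidence of donor chimerism at the planned 3-4 week study, whatever the ANC or cellularity. Report those with and without ANC recovery as two subtypes.
2. **Delayed or poor graft function:** donor-positive patients without ANC recovery by D+28, listed as their own category and not as graft failure.
3. **Marrow cellularity:** kept as a descriptive item where a marrow was done.
4. **Secondary graft failure:** tabulate events by donor chimerism status where available, so that neutropenia with retained donor cells can be told apart from graft loss.

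Items 1 and 2 use the ANC and the first chimerism study already in the plan. Item 4 is limited to available results because only the first chimerism study has a stated time. The cost is that the primary graft-failure rate may look slightly less favourable.

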1.0 Objectives

Primary Objective:

To compare the progression-free survival of adding Pacritinib prior to standard of care allogeneic stem cell transplantation (SOC Allo TP) conditioning with Fludarabine and Busulfan AUC of 4000 microMol-min per day to historical controls in patients with myelofibrosis.

Secondary Objectives:

To evaluate safety and efficacy of this therapy as determined by:

- 1.1 Neutrophil and platelet engraftment.
- 1.2 Non-relapse mortality at one year post transplant.
- 1.3 Overall survival at one year post transplant.
- 1.4 Liver and spleen response to Pacritinib.
- 1.5 Immune recovery.
- 1.6 Quality of life and symptom score.
- 1.7 Primary and secondary graft failure.
- 1.8 Complete remission.
- 1.9 Relapse.

To evaluate the use of marrow specific quantitative MRI (qMRI) sequences in assessment of disease burden, including:

- 1.10 Diffusion-weighted imaging (DWI) with apparent diffusion coefficient (ADP) maps
- 1.11 Marrow fat quantification sequences

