5.0 Evaluation During Study

5.1 Disease Assessment Prior to Start of Pacritinib (baseline):

- a) Patient medical history and physical examination including measurement of liver and spleen size by physical examination or imaging (MRI or CT or ultrasound if possible) with addition of marrow-specific MRI sequences.
- b) CBC, differential and platelet count
- c) Bone marrow aspiration and biopsy
- d) Chemistry panel
- e) Serology for CMV, HBV, HCV and HIV
- f) B-HCG in women of childbearing potential
- g) 2 D echo, EKG
- i) Pulmonary function tests with DLCO
- j) Chest x-ray
- k) MF symptoms questionnaire (Appendix D.)
- I) Fact BMT questionnaire (Appendix E.)
- m) Blood for immunological profile if patient agrees to consent to optional study.

5.2 Follow up each month while on Pacritinib:

Patients will come to MDACC once each month to pick-up the next month's Pacritinib and have the following done. The monthly visits will continue as long as patient is taking Pacritinib.

- a) Medical history and physical examination
- b) CBC, differential and platelet count
- c) Chemistry panel
- d) EKG

Cycle 1 only: Day 14 (+/- 2 days) CBC, differential and platelet count and chemistry panel. These can be drawn locally and results sent to MDACC. The PI/treating physician must review outside lab results, determine clinical significance, sign and date the outside lab results.

Cycle 1 only: During week 2, study personnel will call patient about any new symptoms.

Patients treated on this protocol may require supportive care treatment (concomitant medications). These medications are considered standard of care and have no scientific contribution to the protocol; therefore no data will be captured on various medications needed or their side effects.

5.3 Within about 7 days after completion of Pacritinib (but before transplant):

- 1) Physical examination including measurement of liver and spleen size by physical examination or imaging (MRI or CT or ultrasound if possible).
- 2) EKG
- 3) Bone marrow aspiration and biopsy

5.4 Post-transplant Evaluations:

- 5.4.1 Post-transplant evaluations will follow our standard practice and are done to monitor engraftment and disease status.
- 5.4.2 Additional post-transplant follow-up specific to this study at approximately 1, 3, 6, and 12 months post-transplant:
 - 1) At around 3 months:
 - Measurement of liver and spleen size by physical examination or imaging (MRI or CT or ultrasound if possible).

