All life-threatening or fatal events, that are unexpected, and related to the study drug, must have a written report submitted within **24 hours** (next working day) of knowledge of the event to the Safety Project Manager in the IND Office.

The investigator will inform CTI Biopharma of any SAE within 24 hours of being aware of the event via email and/or fax.

Unless otherwise noted, the electronic SAE application (eSAE) will be utilized for safety reporting to the IND Office and MDACC IRB.

Serious adverse events will be captured from the time of the first protocol-specific intervention, until 14 days after the last dose of drug, unless the participant withdraws consent. Serious adverse events must be followed until clinical recovery is complete and laboratory tests have returned to baseline, progression of the event has stabilized, or there has been acceptable resolution of the event.

Additionally, any serious adverse events that occur after the 14 day time period that are related to the study treatment must be reported to the IND Office. This may include the development of a secondary malignancy.

Reporting to FDA:

Serious adverse events will be forwarded to FDA by the IND Sponsor (Safety Project Manager IND Office) according to 21 CFR 312.32.

Adverse events known to be related to SOC ALLO TP will not be recorded in PDMS.

List of most common expected adverse events related to SOC ALLO TP:

- 1. Infections in the presence or absence of neutropenia: fungal, bacterial and or viral infections.
- 2. Fever: Non-neutropenic or neutropenic without infection
- 3. Acute graft versus host disease (aGVHD): most commonly manifested by skin rash, diarrhea and abnormal liver function tests could also present with some degree of fever, upper gastrointestinal symptoms (nausea and vomiting) mucositis and eye dryness.
- 4. Gastrointestinal (GI tract): the GI tract manifestations could be not only due
- 5. to direct damage from the preparative regiment but also be a manifestation of GVHD or infections. Therefore, the time course and its presentation are crucial when assessing these as adverse events. Nausea/vomiting, mucositis, diarrhea when presented within first 7 to 10 days most likely will be related to the preparative regimen.
- 6. Skin rash: not related to GVHD could be caused by chemotherapy used for the preparative regimen or antibiotics used a supportive treatment.
- 7. Transaminitis: liver function test elevation.

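### Secondary graft failure is defined by three consecutive days of low ANC alone, with no evidence of graft loss required, so temporary neutropenia with preserved donor chimerism can be counted

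*Combined protocol and SAP*

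**What the plan says.** Section 1.0 lists "Primary and secondary graft failure" as secondary objective 1.7. Section 6.2 defines three related endpoints:

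- Neutrophil engraftment needs ANC of at least 0.5 × 10⁹/L for 3 consecutive days, together with "evidence of donor chimerism by D+28 (the first chimerism study will be done 3-4 weeks post-transplant".
- Primary graft failure is failure to reach that ANC by day 28, "with <10% cellularity on bone marrow biopsy and no evidence of donor chimerism".
- For the secondary form: "Secondary graft failure is defined as a sustained declined of ANC" below 0.5 × 10⁹/L "for 3 consecutive days after initial documented engraftment with no evidence of disease progression".

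On the data that might explain a low count, Section 5.2 describes supportive medications as standard of care and says "therefore no data will be captured on various medications needed or their side effects". Section 8.0 keeps adverse events known to be related to the standard transplant out of PDMS. The first item on its list of such expected events is "Infections in the presence or absence of neutropenia: fungal, bacterial and or viral infections". Section 5.4.1 leaves post-transplant evaluation to standard practice, aimed at engraftment and disease status.

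**The concern.** Graft failure means that the donor graft did not take or was lost. The primary definition tests this directly, through chimerism and the marrow. The secondary definition tests only a blood count and sets aside only one alternative explanation, disease progression. A patient reaches the point of being at risk by having shown donor cells at engraftment, yet nothing asks whether those cells have gone.

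At stake is the meaning of objective 1.7. The background (Section 2.4, on impediments to transplant) presents graft failure and weak grafts as a major problem in myelofibrosis, and better engraftment as one reason to give a JAK2 inhibitor beforehand. If the count mixes lost grafts with temporary neutropenia, a reader cannot tell what it says about that rationale, and the primary and secondary figures reported side by side measure different things.

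**Working it through.** The plan states no expected rate, reference rate or threshold for graft failure, so there is no figure of its own to reproduce. The check compares the definitions and then sizes one misclassified case.

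**1. The three definitions in Section 6.2 side by side**

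| Endpoint | ANC criterion | Donor chimerism | Marrow | Exclusion |
|---|---|---|---|---|
| Neutrophil engraftment | ≥0.5 × 10⁹/L, 3 consecutive days | must be present by day 28 | none | none |
| Primary graft failure | not ≥0.5 × 10⁹/L for 3 consecutive days by day 28 | must be absent | cellularity <10% | none |
| Secondary graft failure | <0.5 × 10⁹/L, 3 consecutive days after engraftment | not mentioned | not mentioned | disease progression |

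**2. Applying the secondary rule.** Take a patient who engrafted, remains donor-chimeric, has no progression, has ANC below 0.5 × 10⁹/L on three consecutive days, and then recovers. Every stated condition is met and no exclusion applies, so the patient is counted. The same chimerism result would rule out primary graft failure.

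**3. Does the word for a sustained decline help?** The only duration given is the 3 days. The engraftment definition uses the same qualifier with the same 3 days, so it does not signal a longer period or non-recovery.

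**4. Could such cases be removed later from the study data?** Three provisions stand in the way.
- Section 5.2 captures no data on supportive medications or their side effects. The sentence stands among the pacritinib visits but is worded for patients treated on the protocol generally.
- Section 8.0 does not record transplant-related adverse events, infections included, in PDMS.
- Section 8.1 collects pacritinib-related events for active treatment plus 14 days, while Section 4.1.3 stops pacritinib 21 days before conditioning. That window closes 21 − 14 = 7 days before conditioning starts.

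Medical records could be searched, but without a prespecified rule that would be judgement after the fact in a single-arm trial.

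**5. Size of one case.** Input: at least 21 evaluable patients (Section 6.0).
- Step per misclassified patient: 1/21 = 4.8 percentage points (smaller if more than 21 are evaluable).
- Expected extra cases = 21 × q, where q is the share of patients with such an episode. The documents give no q. The values below are assumptions for illustration only: q = 5% gives 1.05; q = 10% gives 2.1; q = 20% gives 4.2.
- Effect on the reported estimate with no true failures, exact (Clopper–Pearson) 95% intervals:
  - 0/21 = 0%; upper limit 1 − 0.025^(1/21) = 16.1%.
  - 2/21 = 9.5%; lower limit is the 2.5% point of Beta(2, 20) = 1.2%; upper limit is the 97.5% point of Beta(3, 19) = 30.4%.

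**The case against.** **The rule is not as loose as any three low counts.** A reader might summarise it that way, but it requires consecutive days, after documented engraftment, in a patient without progression. This limits which episodes qualify. It does not require evidence of graft loss.

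**The competing cause is inferred.** The list in Section 8.0 names infections with or without neutropenia. It does not say that infection or drugs are expected to cause neutropenia after engraftment. This stands: that such episodes will occur is clinical inference, and the documents give no frequency.

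**Inflation is not demonstrated.** A reader might conclude that the rate is inflated. The documents do not support that as fact. The definition can also miss loss of donor cells when ANC is preserved, which pulls the other way, so the net direction is a reasonable inference only.

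**There is no suitable yardstick in the protocol.** It is tempting to compare with Section 2.3, where in a cited reduced-intensity study "13% of patients needed stem cell boost for graft failure or weak graft or declining chimerism"; 0.13 × 21 = 2.7 patients. That is a different quantity: it counts boosts given for several reasons, not secondary graft failure, and cannot serve as a benchmark.

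**The endpoint is descriptive.** Section 6.0 sets no test, threshold or historical rate for graft failure, and the estimate is imprecise at n = 21 under any definition. This also stands. It rules out a claim that a formal conclusion would be reversed, but a descriptive rate should still count the event it names.

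**Conclusion.** The definitional gap is established from the text: under Section 6.2 as written, a patient with preserved donor chimerism and a temporary neutropenia from another cause is scored as a secondary graft failure, although the trial's own primary definition would require evidence that the graft is absent. The rate for objective 1.7 may therefore be inflated, by 4.8 percentage points per such case at 21 evaluable patients. The number of cases cannot be stated from the documents, and the illustrative range above rests wholly on assumed frequencies. The study database would not reliably allow these cases to be identified afterwards.

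The point is confined to one descriptive secondary endpoint. Progression-free survival, its 5% one-sided test and the sample size of 21 do not depend on it.

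**What to change.** Amend the secondary graft failure definition in Section 6.2 as follows:

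- Keep the ANC criterion, the engraftment condition and the progression exclusion, and add documented loss of donor chimerism, worded to match the primary graft failure rule.
- Use the chimerism and marrow results from standard post-transplant monitoring that lie nearest to the ANC fall, and state in advance how near they must be to count.
- Report two further categories separately: ANC below 0.5 × 10⁹/L for 3 consecutive days with preserved donor chimerism, and the same with no chimerism result available.
- Do not make need for a stem cell boost a defining criterion, since the endpoint would then depend on a treatment decision.

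Cost and limits: one added data item, the chimerism result and its date for each qualifying ANC episode. Section 6.2 fixes only the first chimerism study, at 3–4 weeks, and no section schedules one when ANC falls, so some episodes may lack a concurrent result; the third category makes this visible. The failure count may be smaller than under the present wording. The change does not capture loss of donor cells with preserved ANC, which the present definition also misses.

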Complete remission is defined as per response criteria defined by European Myelofibrosis network (Appendix G.).

Relapse will be recorded by the day of detection.

Overall Survival is defined as the interval between day of transplant and day of death.

Sample Size and Power

The historical 1-year PFS rate in this population is 61%. Our goal is to improve this to 80%. We expect to enroll patients over a 3-year period and follow all patients for 1 year after enrollment is complete. Under these assumptions, assuming exponentially -distributed PFS times, and using a one-sided exponential MLE test with a 5% Type I error rate, we will need 21 patients to have 80% power to detect an increase in 1-year PFS to 80%. We will provide the 1-year PFS rate along with a corresponding 95% interval and test the hypothesis that it is greater than 61% using an exponential MLE test. Only patients who undergo transplant with a matched related or at least 7/8 matched unrelated donor will be include in this analysis.

Secondary Analyses

We will use the Kaplan-Meier method to estimate the distribution of secondary time-to-event (TTE) endpoints overall survival, time to neutrophil engraftment, and time to platelet engraftment. We will use Cox regression analysis will be used to assess the association between TTE endpoints (including PFS) and clinical and disease covariates of interest. We will assess the cumulative incidence of non-relapse mortality (NRM) and disease relapse in a competing risks framework and use the method of Fine and Gray to fit regression models to these endpoints.

Liver and spleen response to pacritinib will be measured by the change in the size of each organ measured below the coastal margin in the mid-clavicular line by palpation and imaging.

Quality of life (QOL) will be assessed using the QOL FACT BMT, and symptom score will be assessed by the MPD symptom score. Changes in these over time will be analyzed by a generalized linear mixed model (GLMM) approach to account for intra-patient correlation.

For the immune studies, various cell subsets and cytokine levels will be assessed at several timepoints. GLMM or other appropriate statistical models will be fit to assess changes over time in these parameters and relationships with other endpoints.

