7.0 Criteria for Removal from the Study

- 7.1 Any toxicity that is deemed unacceptable by the study PI.
- 7.2 Disease progression.
- 7.3 Lack of compliance with the requirements of the study.
- 7.4 Withdrawal of consent.
- 7.5 After one year of transplant.

7.6 No matched related or less than 7/8 matched unrelated donor.

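### The 80% power assumes follow-up to one year after enrollment closes, but item 7.5 removes patients one year after transplant; if PFS is censored there, power is about 54–60%

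*Combined protocol and SAP*

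**What the plan says.** Section 6.0, Sample Size and Power, gives the follow-up behind the calculation: "We expect to enroll patients over a 3-year period and follow all patients for 1 year after enrollment is complete". On that basis, with exponential PFS times and a one-sided 5% exponential MLE test, it concludes "we will need 21 patients to have 80% power to detect an increase in 1-year PFS to 80" per cent. The null is given as "The historical 1-year PFS rate in this population is 61" per cent. Section 6.1 starts PFS at transplant.

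Section 7.0 lists among the reasons for leaving the study "7.5 After one year of transplant". Section 5.4.2 sets "Additional post-transplant follow-up specific to this study at approximately 1, 3, 6, and 12 months post-transplant", with nothing study-specific after that.

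Two other passages bear on what happens after removal. Section 5.4.1 says "Post-transplant evaluations will follow our standard practice and are done to monitor engraftment and disease status", without an end date. Section 7.0 also removes patients for "7.2 Disease progression", although Section 6.2 says "Overall Survival is defined as the interval between day of transplant and day of death". Some status after removal is therefore already needed for a secondary endpoint.

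**The concern.** The exponential MLE test estimates the hazard as events divided by person-time, and its precision depends mainly on the number of events. Under Section 6.0 a patient is followed for between one and about four years. Under item 7.5, read as the end of data collection, nobody is followed beyond one year. The two rules give very different event counts from the same 21 patients.

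Apart from the Section 6.0 sentence, nothing in the plan says PFS is collected after removal, and no PFS censoring rule is stated. Whoever closes the database must choose a censoring date without guidance, and that choice decides whether the primary test has about its stated power or far less.

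**Working it through.** **Inputs.** From Section 6.0: 1-year PFS of 61% (null) and 80% (alternative), exponential times, one-sided 5%, n = 21, 3 years of enrollment plus 1 year. From item 7.5: removal at 1 year after transplant. Assumptions: uniform accrual, no other loss to follow-up, and transplant taken as the start of the clock except where stated.

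**Hazards.** λ0 = −ln 0.61 = 0.4943 per year; λ1 = −ln 0.80 = 0.2231 per year.

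**1. Follow-up as Section 6.0 states it (uniform on 1 to 4 years).**
P(event) = 1 − [exp(−λ) − exp(−4λ)] / (3λ).
- Null: 0.682, so 21 × 0.682 = 14.3 events.
- Alternative: 0.417, so 8.75 events.

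The closed-form sample sizes for 80% power are:
- log-hazard scale, null and alternative variances: [(1.645/√0.682 + 0.842/√0.417) / ln(0.4943/0.2231)]² = 17.2
- cube-root scale: 18.3
- hazard scale, both variances: 22.1
- log scale, alternative variance only: 23.4

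The stated 21 lies inside this range.

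**2. PFS censored at one year after transplant.**
- Null: P(event) = 1 − 0.61 = 0.39, so 8.19 events.
- Alternative: P(event) = 1 − 0.80 = 0.20, so 4.20 events.

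**Simulated power at n = 21 (200,000 trials).** The last column sets the critical value so that the type I error is exactly 5%. The uncalibrated tests have simulated type I error between 0.035 and 0.051.

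| Follow-up | Events under alternative | Log-Wald | Score | Likelihood ratio | Calibrated to 5% |
|---|---|---|---|---|---|
| As in Section 6.0 | 8.75 | 0.819 | 0.825 | 0.856 | 0.858 |
| Censored at 1 year | 4.20 | 0.543 | 0.572 | 0.594 | 0.602 |
| Later status for half the patients (illustrative assumption) | (8.75 + 4.20)/2 ≈ 6.5 | 0.699 | 0.710 | 0.760 | 0.756 |
| Common cut-off 1 year after last evaluable transplant | 8.4 | 0.807 | 0.812 | 0.845 | 0.847 |

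**Exact cross-check at one year.** With 21 patients, rejecting when at least 17 are progression-free has type I error 0.0449 and power 0.586.

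**Sample size under a one-year cap.** The calibrated test reaches 0.79 at n = 34 and 0.81 at n = 36. The log-Wald test reaches 0.793 at n = 38 and 0.819 at n = 40. About 36–40 evaluable patients would be needed for 80% power.

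**Lag to transplant.** Section 4.1.2 puts transplant 60 to 180 days after pacritinib starts. If the clock runs from enrollment and this lag is uniform, with no cap, power is 78–82%. The lag alone is a minor matter.

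**Could 21 have been derived for one-year follow-up?** The untransformed hazard-scale formula with alternative variance gives [(1.645 + 0.842) × 0.2231 / (√0.20 × 0.2712)]² = 20.9, where 0.2712 = 0.4943 − 0.2231. But that test has simulated type I error 0.104, not 0.05, and power 0.752. Under the 1-to-4-year follow-up the same formula needs only 11 patients.

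**The case against.** The strongest reply is that removal from study need not stop outcome collection. Section 6.0 is the only passage that speaks directly to follow-up for the primary analysis, and it is explicit. Sections 5.4.1, 7.2 and 6.2 point the same way: disease monitoring has no end date, and survival must be known after removal for progression. Section 2.4 adds that the center's earlier cohort, the planned comparator, was followed for up to 6 years with 3-year outcomes reported. If PFS is collected on that basis, the stated power stands. This is a fair reading, and it is why the shortfall is conditional. The plan does not say it, however, and item 7.5 taken at face value says otherwise.

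Second, since the target is a 1-year rate, one year of follow-up might seem enough. It is enough to estimate the rate. It does not give 80% power: both the exponential test and the exact binomial test stay at about 60% or below.

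Third, the origin of 21 is uncertain, because none of the closed forms for 1 to 4 years rounds to it and one formula for fixed one-year follow-up does. That stands as an uncertainty, but a test with about 10% type I error does not meet the plan's stated 5%.

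Fourth, Table 2 reports 61% as a 3-year event-free survival, so the null itself can be questioned. That is a separate matter. All figures here take the plan's 61% and 80% as given.

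**Conclusion.** The concern holds. It is a conflict between two follow-up rules, not a slip in the power calculation: on the Section 6.0 inputs, 21 patients and 80% are approximately right. If item 7.5 sets the censoring date, expected events under the alternative fall from 8.75 to 4.20. Like for like, at an exact 5% level, power falls from 86% to 60%; across the tests that hold the level it is 54–60%. A true improvement to 80% would then be missed in roughly 40–46% of such trials. Partial capture of later status gives an intermediate result.

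These figures rest on exponential PFS, uniform accrual and no other loss to follow-up. Confidence is moderate, because the plan does not say which reading was intended. It should be fixed before analysis.

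**What to change.** Reconcile Sections 6.0 and 7.0:

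- State in item 7.5 that it ends study visits only, and that PFS and survival status continue to be collected from routine transplant follow-up until a common cut-off one year after the last evaluable patient's transplant.
- Change the follow-up sentence in Section 6.0 so that the cut-off is tied to the last evaluable transplant rather than to the close of enrollment. This keeps power at 81–85%.
- Add a PFS censoring rule, for example at the last date the patient was known to be alive and progression-free, no later than the cut-off.
- If a one-year cap is intended instead, say so and restate the power in Section 6.0 as about 55–60% for 61% versus 80%.

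The cost is two or three sentences plus some status collection from routine records, or a less favorable stated power. No extra patients or procedures are needed.
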